Based on these data, a comprehensive questionnaire to address QOL issues and health behaviors of melanoma survivors was designed and tested. Then a cross-sectional study of melanoma survivors and population controls was conducted. The goal was to collect data to evaluate the impact of melanoma on long-term survivorship focusing on quality of life ¹⁷ and sun exposure and protection behaviors ¹⁸. A total of 724 melanoma survivors and 660 controls from the parent study completed the survey. Melanoma survivors were diagnosed an average of 9.6 ± 1.0 years prior to completing the survey; the majority (85.6%) had stage I disease, 6.4% had stage II

PROTOCOL TITLE: Wearable device intervention to improve sun behaviors in

melanoma survivors

VERSION DATE: 07/19/2021

disease, 6.6% had stage III disease, and 1.4% had stage IV disease. The most common anatomic site of the tumor was the trunk (35.0%), followed by legs (26.9%), arms (26.4%), and head/neck (11.7%). Almost all (99.3%) had surgery and about one-third had lymph node dissection (34.8%).

Melanoma survivors, compared to controls, reported statistically significant but only slightly higher physical functioning and bodily pain QOL subscale scores than controls and otherwise similar QOL as measured by the remaining six SF-36 subscale scores ¹⁷. Prevalence of anxiety and depression were similar between melanoma survivors and controls.

Our data regarding sun exposure and protection behaviors indicated that long-term survivors of melanoma reported greater use of sun protection behaviors than controls ⁸. Particularly important to this application, however, was the significant subgroup of melanoma survivors (20%) who experienced sunburn in the past year, reported intentional tanning (10%), did not wear a hat (67%) or stay in the shade (52%), and spent more than two hours in the sun on weekends (75%), putting them at elevated risk for future melanomas (Figure 1).

In addition to our expertise on melanoma survivors and sun protection, we also have conducted research in using technology to change behavior. In two large-scale federally funded research studies of physical activity (R01AG023410, R01-HL072947), and one large-scale federally funded study of weight-loss maintenance (R01-CA128211), collaborator [name] employed electronic devices in the form of accelerometer-based actigraphy monitors for collection of objective measures of physical activity. He served

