- Unintended Consequences: we will measure physical activity, depression and anxiety to examine the potential unintended negative consequences of the intervention. Self-reported physical activity, along with other healthy behaviors such as fruit and vegetable consumption, will be ascertained using the American Health Association's Life's Simple 7²⁴. Depression and anxiety will be measured using the Hospital Anxiety and Depression Scale (HADS)²⁵.

4. Study Intervention

4.1. Conceptual Model and Description:

We are adopting the Fogg Behavioral Model²⁶ as our theoretical guide for this intervention, as depicted in the conceptual framework chart (Figure 2). Following the Fogg Behavioral Model, we will address barriers, examine motivators, and provide appropriate triggers to encourage optimal sun protection behaviors in melanoma survivors. The intervention will identify individual barriers that prevent melanoma survivors from optimal sun protection behaviors and then use messages (through website/brochure) to reduce perceived barriers and increase motivation to change. When people are highly motivated to change behavior and have the means to conduct the goal behavior, triggers are employed to prompt action; here, triggers would be messages regarding sun protection and exposure delivered via the wearable device as it detects UVR exposure.

[figure not shown]

Figure 2 Conceptual Framework of the Study
Page 12 of 53

PROTOCOL TITLE: Wearable device intervention to improve sun behaviors in

melanoma survivors

VERSION DATE: 07/19/2021

Intervention Components:

We propose to use a wearable device that monitors UVR exposure to promote optimal sun protection behaviors. This intervention was chosen instead of an information-only website or mobile application because while knowledge is one component of behavior change, the intervention should address barriers, provide motivators and more importantly triggers to ultimately change behavior. In conjunction with the device and its associated mobile application, we will also develop a website that will provide information about the importance of UVR avoidance and protection in the population, in addition to supporting other health behaviors. Both intervention components will be provided to study participants randomized to the intervention group; the control group will receive modified versions of each component.

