Hospital Anxiety and Depression Scale	Secondary outcome (unintended consequence)	Screen for depression and anxiety used frequently in cancer survivors; Likert scale	14	X			X	X
Comorbidities	Background		14	X			X	X
Diagnosis and treatment	Background/ Potential moderators	Year diagnosis, location, stage, treatments received, recurrence, metastasis	18	X				
Fear of recurrence	Background/ Potential moderator	Cancer and health worry	5	X			X	X
Demographics	Background/ Potential moderators	Sex, age, race/ethnicity, education, income, marital status, parent status, family history of cancer, skin phenotype	15	X				
Device use			9		X	X	X	
Device satisfaction			17				X	
Total number of items				198	51	51	167	141

* Time frame: past 4 weeks

** Time frame: past summer

5.3. Study Duration:

While the entire study will take approximately 4 years in total, each participant will only be enrolled for a little longer than 1 year (12-week intervention implementation period, and follow up survey at 64-weeks).

5.4. Individually Identifiable Health Information:

HealthPartners will obtain patient name, address, email address, and telephone number based on melanoma diagnosis to contact potentially eligible participants. Among those who agree to participate in the study, we will obtain signed Health Insurance Portability and Accountability Act (HIPAA) authorization forms to seek data from HealthPartners and store

PROTOCOL TITLE: Wearable device intervention to improve sun behaviors in melanoma survivors

VERSION DATE: 07/19/2021

information regarding their melanoma diagnosis, including date of diagnosis and disease stage. These data will supplement the self-reported data.

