Statistical analysis will focus on evaluating the efficacy, unintended consequences and implementation of the intervention in this RCT. The main analysis of the primary outcome (self-reported overall sun protection score) will be a two-sample two-sided two-sample t-test comparing scores at the end of the intervention period (12 weeks) between intervention and control groups. Randomization should result in two groups that are similar for patient characteristics and other extraneous factors that may influence sun exposure and protection behaviors, however, we will compare the randomized groups by Wave, gender, age, stage of disease, device use (low/high), and baseline measures of sun protection and exposure behaviors using two-sample t-tests and Chi-squared tests to identify potential confounding factors which may not be balanced between the two groups. We will supplement the primary analysis with a multivariate linear regression model to account for any identified differences at baseline. A secondary analysis will explore changes in the sun protection score over the intervention period (baseline, weeks 4, 8 and 12) using a mixed effects regression model. This analysis will not be completed until both Waves have been conducted.

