Secondary analyses will focus on each self-reported sun protection behavior separately, sunburns, intentional tanning, skin cancer knowledge, and physical activity and health behaviors by comparing the intervention and control participants over the study intervention period and 1 year post-completion. Analyses will be conducted using Chi-squared and t-tests as appropriate for univariate analyses at each time point and logistic and linear regression models for multivariate analyses. Daily UVR data (minutes of UVR exposure per day) will be summarized using the area under the curve (AUC) over the 12 week intervention period. Proper transformation (e.g. log-transformation) will be applied if the AUC data are skewed. The two groups' AUC will be compared using similar methods as proposed above. The association between sun exposure and its potential moderating effect on sun protection behaviors during the intervention will be investigated using linear mixed effects models including main and interaction effects, adjusting for potential confounders. To address any potential intervention effects in the control group, we will compare the baseline and post-intervention sun protection behaviors scores using paired t-tests, stratifying by randomization group. The proportions of survivors in the intervention and control groups with potentially clinically significant depression and anxiety will be compared using Chi-squared tests and supplemented with multivariate logistic regression models. Finally, descriptive statistics will be used to summarize the implementation metrics

PROTOCOL TITLE: Wearable device intervention to improve sun behaviors in

melanoma survivors

VERSION DATE: 07/19/2021

both across and within randomization group both between Waves 1 and 2 and after completion of the study.

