Appendix: Summary of Protocol Changes and Rationale – 01/27/2020

Major changes:

1. The original version of this protocol was funded by the American Cancer Society. We also received funding for usability and a pilot study version of this proposed work from the Melanoma Research Alliance (protocol STUDY00002107/2018NTLS002). We negotiated to combine the funding to support one larger study to increase our power for experience of sunburn during the intervention period, a key secondary outcome. Therefore, we have increased the sample size here from 248 to 368 (184 each wave/summer) and we will formally close the previous pilot study with the CPRC, IRB and CT.gov and add the Melanoma Research Alliance as a funding source for this protocol. The PI discussed this plan of action with [name] on 1/24/2020 who agreed this would likely be the best path from the IRB perspective.
2. After our usability testing we have decided to switch to a different wearable device than originally proposed. This device, Shade, was developed in collaboration with the NIH NCI and has been shown to be significantly more accurate than our previously proposed device. One disadvantage of this device is that it does not objectively measure physical activity as the previous device did and therefore those pieces were removed from the protocol. We will rely on self-report measures of physical activity to test our secondary hypotheses related to physical activity. Additionally, this device is significantly more expensive than the previously planned device and therefore participants will be asked to return the device at the end of the intervention period and be provided gift cards throughout the study as incentive instead. They will be provided up to \$120 in gift cards if they complete all study procedures (\$20 baseline survey, \$10 week 4 survey, \$10 week 8 survey, \$60 return device and complete week 12 survey, \$20 complete week 64 survey).
3. As this is a minimal risk study, we have removed the during-study monitoring of anxiety and depression. We have found in another study of cancer survivors that this monitoring and sending of letters often confuses and distresses participants. We will plan, however, to examine whether rates of anxiety and/or depression rise during the intervention period (week 12 vs. baseline) following Wave 1. While we do not expect that to be the case, should it happen we will proactively monitor in Wave 2.

Minor changes:

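### The between-arm HADS analyses are binary only, with no use of the score and no stated baseline adjustment, which costs sensitivity to a named harm

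*Combined protocol and SAP*

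**What the plan says.** Section 3.2 lists depression and anxiety, measured with HADS, among the secondary outcomes, and gives the purpose: "to examine the potential unintended negative consequences of the intervention". Table 2 in section 5.2 describes the instrument as "Screen for depression and anxiety used frequently in cancer survivors; Likert scale", with 14 items at weeks 0, 12 and 64. The baseline survey precedes randomization, so a pre-randomization score will exist for each participant who answers the items.

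Section 15.3 has one sentence on comparing the arms: "The proportions of survivors in the intervention and control groups with potentially clinically significant depression and anxiety will be compared using Chi-squared tests". It goes on to say that these tests will be "supplemented with multivariate logistic regression models". The cut-off, the time point and the covariates are not stated. The earlier sentence in 15.3 that allows t-tests as well as Chi-squared tests covers a list of secondary outcomes that does not include anxiety or depression. The variables to be compared between arms for imbalance end with "device use (low/high), and baseline measures of sun protection and exposure behaviors"; baseline HADS is not among them.

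The appendix (Summary of Protocol Changes, major change 3) records that monitoring of anxiety and depression during the study was removed. It adds a plan to "examine whether rates of anxiety and/or depression rise during the intervention period (week 12 vs. baseline) following Wave 1", with monitoring in Wave 2 if rates rise. That check is also on rates, and the arms are not mentioned.

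**The concern.** Every planned HADS analysis starts by reducing the score to a yes/no classification. Two kinds of worsening then disappear: a rise that stops short of the cut-off, and any deterioration in a participant who was already above it. People above the cut-off both before and after add to the counts in each arm and say nothing about change.

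The plan treats its primary score more fully. The sun protection index gets a comparison of means, a mixed model that includes baseline, and paired comparisons with baseline. The psychological outcome, which the protocol itself names as a possible harm, gets none of these, although the data for them are collected. With monitoring during the study removed, the trial-level analysis carries most of the task of detecting such harm. Low sensitivity matters more for a harm than for a benefit, because a null result is easily taken as reassurance.

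**Working it through.** **1. The plan's own figures.** Section 15.2 expects 314 participants with week 12 data (0.85 × 368 = 312.8), so 157 per arm at 1:1, two-sided 0.05.

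- Sunburn, 20% vs 10%. Null SE = √(0.15 × 0.85 × 2/157) = 0.0403. Alternative SE = √((0.20 × 0.80 + 0.10 × 0.90)/157) = 0.0399. Power = Φ((0.10 − 1.96 × 0.0403)/0.0399) = Φ(0.53) = 0.70. Stated: 70%.
- Primary outcome, effect size 0.40. Power = Φ(0.40/√(2/157) − 1.96) = Φ(1.58) = 0.94. Stated: 95%.

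Both agree, so the same formulas serve for HADS.

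**2. HADS inputs.** The documents give none. Section 2.2 says "Prevalence of anxiety and depression were similar between melanoma survivors and controls", without a rate. The following are assumptions: subscale score near normal, rounded and bounded at 0-21, mean 4-6, SD 3.7, cut-off 8, correlation between baseline and follow-up 0.5-0.7, 157 per arm.

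**3. Uniform worsening of 1 point, by formula.** With whole-number scores, 8 or more means above 7.5.

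- Proportions, control mean 4: control P(Z > 3.5/3.7) = 17.2%, intervention P(Z > 2.5/3.7) = 25.0%. Power = Φ((0.0775 − 1.96 × 0.0460)/0.0458) = 0.39.
- Proportions, control mean 6: 34.3% vs 44.6%. Power = Φ((0.1037 − 1.96 × 0.0552)/0.0549) = 0.47.
- Score, unadjusted: SE = 3.7 × √(2/157) = 0.418. Power = Φ(1/0.418 − 1.96) = 0.67.
- Score, baseline-adjusted: SE = 0.418 × √(1 − r²), which is 0.362 at r = 0.5 and 0.298 at r = 0.7. Power = 0.79 and 0.92.

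**4. The same by simulation.** Rounding and the floor at 0 lower the score results slightly.

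| Analysis | Power, uniform +1 point |
|---|---|
| Chi-squared on proportions | about 38-49% |
| Binary, adjusted for baseline HADS | about 44-62% |
| Score, unadjusted | about 63-67% |
| Score, adjusted for baseline | about 76-90% |

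**5. A harm shape less favorable to the mean.** Suppose 10-15% of intervention participants worsen by 6 points and the rest do not change, so the average shift is 0.10 × 6 = 0.6 to 0.15 × 6 = 0.9 points. Power is about 16-49% for Chi-squared and 34-78% for the adjusted score. With 10% affected every method is weak, but the adjusted score still leads.

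**6. A different parameterization.** Take a uniform 0.3 SD worsening, with control prevalence from 5% to 25%. Chi-squared has 28-52% power, the unadjusted score 76%, and the adjusted score 87% (r = 0.5) to 96% (r = 0.7). The shift detectable with 80% power is 0.58 to 0.41 SD for the cut-off, against 0.27 to 0.23 SD for the adjusted score.

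**7. People already above the cut-off.** On the assumptions in step 2, about 41-66% of control participants above the cut-off at follow-up were above it at baseline. Allocation follows the baseline survey, so the same share is expected in both arms before any intervention effect. They dilute the contrast and do not shift it.

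**The case against.** The strongest case for the plan is that HADS is there as a screen, and that the share of probable cases is a clinically readable measure of harm. A 1-point shift in the mean is a different quantity, and nothing in the documents calls it meaningful. That is a sound reason to keep the proportion. It is not a reason to leave out the score, because the two can be reported together.

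Second, the logistic models might include baseline HADS. They might; the plan neither says so nor rules it out. On the generous reading the outcome stays binary, and power rises only to the range shown for the adjusted binary analysis.

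Third, the size of the gain rests on assumed values, and a uniform shift suits a comparison of means. This stands as a caution on the figures. The ranking survives concentrated harm; the size of the gap does not.

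A reader might go further and infer three things that the documents do not support. One is that harm is judged only at follow-up, with no reference to baseline; the Wave 1 check compares week 12 with baseline. Another is that participants above the cut-off before randomization bias the comparison; randomization balances them. The third is that a non-significant test will be reported as absence of harm; no passage sets such a rule.

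**Conclusion.** The point holds as one of lost sensitivity. The between-arm HADS analyses are binary, their cut-off, time point and covariates are unstated, and no analysis of the score is planned. On the assumed values, moving from Chi-squared on the proportion to the baseline-adjusted score takes power from a little under one half to between about three quarters and nine tenths for a uniform 1-point shift. The gain is smaller in absolute terms when harm falls on few participants. Mean, SD, cut-off, correlation and shape of harm are all assumptions, so these figures illustrate the direction and rough size of the loss and are not estimates for this trial.

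This is a secondary outcome in a study described as minimal risk, and the primary conclusion is not affected. The change is still worth making, because the outcome is a named harm and the data needed are already being collected.

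**What to change.** In 15.3, add a between-arm comparison of the anxiety and the depression subscale scores at weeks 12 and 64, each adjusted for its baseline score and reported as a difference with a 95% CI. Keep the proportion above the cut-off; state the cut-off and the time points, and put baseline HADS in the logistic model. Report by arm the number of participants newly above the cut-off since baseline.

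No new data, visits or survey items are needed. The cost is revised wording in 15.3 and a few more models and estimates to report.

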13.2. Reproduction Risks: N/A

13.3. Risks to Others: N/A

14. Potential Benefits to Participants

14.1. Potential Benefits:

There are likely no direct benefits to individual participants. Individuals in both groups may increase their activity level during the study period due to prompting from the device. Should the intervention be effective, participants may increase their awareness about melanoma and risk factors for a second melanoma and may decrease their own risk through improved UVR exposure protection habits.

15. Statistical Considerations

15.1. Data Analysis Plan:

All questionnaires have been previously developed and implemented and will be scored using standard methods.

15.2. Power Analysis:

Anticipating 85% of those recruited to the study complete the 12 week follow-up survey, a sample size of N=314 participants with outcome data is expected. A sample size of 314 will achieve 95% power to detect an effect size of 0.40 between intervention and control groups using a two-sided two-sample t-test assuming a significance level of 0.05. The effect size is similar to that found in an intervention to promote sun protection behaviors in high-risk individuals with the same primary outcome ¹⁹. Importantly, it will also achieve 70% power to compare report of sunburn during the intervention period between the two groups (detect 20% of the control participants reporting a sunburn – as seen in our preliminary data - and 10% of the intervention participants reporting a sunburn) as statistically significant at 0.05 significance level.

15.3. Statistical Analysis:

PROTOCOL TITLE: Wearable device intervention to improve sun behaviors in melanoma survivors

VERSION DATE: 07/19/2021

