We plan to perform all primary statistical analyses following intention-to-treat (ITT) procedures. That is, all subjects allocated to a treatment or intervention will be followed up, evaluated, and analyzed as members of that group or treatment arm regardless of their compliance with the assigned treatment. While it is not expected that participants will be incorrectly assigned, some may not use the device and certain features. For that reason, we will also summarize device use and consider sensitivity analyses exploring the intervention effect using per-protocol methods (incorporating device use) as opposed to ITT. *A priori*, we anticipate that the amount of use of the intervention will predict sun protection and exposure behaviors, though we will likely be underpowered for this analysis.

Every effort will be made to encourage participants' compliance and data completeness. Nevertheless, we expect some amount of missing data. We plan to perform a comprehensive missing data analysis employing statistical methods that are valid under different missingness assumptions to determine if conclusions are sensitive to missing data. The primary missing data method will be multiple imputation using the Markov Chain Monte Carlo (MI-MCMC) method^{36,37} assuming that data are missing at random—that is, the probability that an observation is missing can depend on the observed data but not on the missing data. We will include appropriate baseline variables into the MCMC procedure to make the conditional independent missing assumption less stringent. If the treatment group is associated with missingness, we will conduct multiple imputation for each treatment group separately³⁸. The MI-MCMC method allows arbitrary missing patterns including intermittent missing and dropout. We will also perform a simple imputation analysis as a sensitivity analysis; specifically, the linear interpolation method will be used for intermittent missing (e.g., when people forget to charge or wear the device), while the last week average value carried forward method will be used for dropouts, assuming that the average of the last 7 days' data will be a good estimate of the missing data.

15.4. Data Integrity:

Data will be entered and stored in REDCap. Data will be reviewed for completeness and cleanliness on an ongoing basis by the study coordinator and statistician.

16. Confidentiality

PROTOCOL TITLE: Wearable device intervention to improve sun behaviors in

melanoma survivors

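### Section 15.3 splits imputation by arm only if arm predicts missingness. That is the wrong condition: if the pooled model omits arm, an imputed week-12 effect shrinks by up to about 15% at the planned dropout.

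*Combined protocol and SAP*

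**What the plan says.** The main analysis in section 15.3 is a two-sided t-test "comparing scores at the end of the intervention period (12 weeks) between intervention and control groups". It mentions no imputation. Section 15.2 bases power on completers: "a sample size of N=314 participants with outcome data is expected".

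Later in section 15.3, under missing data:

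- "The primary missing data method will be multiple imputation using the Markov Chain Monte Carlo (MI-MCMC) method", under a missing-at-random assumption.
- On predictors: "We will include appropriate baseline variables into the MCMC procedure to make the conditional independent missing assumption less stringent". No variable is named, so neither arm nor the week-4 and week-8 scores are either listed or excluded.
- On arm: "If the treatment group is associated with missingness, we will conduct multiple imputation for each treatment group separately". No test or threshold for an association is given. The same text is repeated in the table of contents.
- On scope: "The MI-MCMC method allows arbitrary missing patterns including intermittent missing and dropout".
- On purpose: "employing statistical methods that are valid under different missingness assumptions to determine if conclusions are sensitive to missing data".
- On the analysis set: "We plan to perform all primary statistical analyses following intention-to-treat (ITT) procedures".

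**The concern.** Whether arm predicts who is missing and whether arm predicts the score are separate questions. The second one decides whether the imputation must know about arm. If the intervention works, arm predicts the week-12 score. A model blind to arm then draws the missing values in both arms toward a common mean, and the imputed difference shrinks.

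Equal dropout is exactly the case in which the rule keeps the pooled model, and equal dropout gives no protection. Shrinkage is governed mainly by how much is missing overall and hardly at all by imbalance between arms.

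If the primary test uses imputed data, the cost is an understated effect and some lost power. If imputation is only a robustness check, a smaller imputed difference could be read as sensitivity to missing data when the imputation model produced it. An undefined trigger also leaves a choice to be made after the data are seen.

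**Working it through.** **Inputs from the protocol.** 368 randomised 1:1, so 184 per arm (sections 5.1 and 5.2). 85% complete week 12, so 15% are missing. Effect size 0.40, two-sided alpha 0.05, 314 with outcomes (section 15.2). Scores at weeks 0, 4, 8 and 12 (section 6.2).

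**Assumptions not in the protocol.** Equal correlation ρ between visits, 0.5 to 0.7 (0.4 to 0.8 for the wider range). Missingness unrelated to outcome. Effect by visit as stated below. Two dropout patterns: all 15% lost after week 8 (late), or 5% / 10% / 15% missing at weeks 4 / 8 / 12 (staggered).

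**Step 1: reproduce the plan's figure.** 368 × 0.85 = 312.8, against 314 stated. With 157 per arm the noncentrality is 0.40 × √(157/2) = 3.54, and noncentral-t power is 94.2%, against 95% stated. Both agree within rounding.

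**Step 2: arm omitted, baseline variables only.** Let d1 and d0 be the missing fractions, and w1 and w0 each arm's share of the observed scores. Imputed values in both arms centre on the pooled observed mean, so

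expected difference = 0.40 × [1 − (d1·w0 + d0·w1)].

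| Missing, arm 1 / arm 0 | Shrinkage | Difference |
|---|---|---|
| 15% / 15% | 0.15 × 0.5 + 0.15 × 0.5 = 15.0% | 0.340 |
| 10% / 20% | 0.10 × 0.471 + 0.20 × 0.529 = 15.3% | 0.339 |
| 5% / 25% | 0.05 × 0.441 + 0.25 × 0.559 = 16.2% | 0.335 |

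Imbalance barely matters, and 15% is not a strict ceiling.

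**Step 3: arm omitted, interim scores in the model.** Observed interim scores carry part of the arm difference into the imputed value. The carried difference is the sum of (pooled regression slope × arm effect) over the visits observed. With a constant 0.40 effect:

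| Scores observed | ρ = 0.5 | ρ = 0.6 | ρ = 0.7 |
|---|---|---|---|
| Baseline | 0 | 0 | 0 |
| Baseline, week 4 | 0.147 | 0.165 | 0.182 |
| Baseline, weeks 4 and 8 | 0.215 | 0.233 | 0.250 |

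- Late loss: 0.85 × 0.40 + 0.15 × (0.215 / 0.233 / 0.250) = 0.372 / 0.375 / 0.378, a shrinkage of 6% to 7%.
- Staggered loss: 0.34 + 0.05 × (sum of each column) = 0.358 / 0.360 / 0.362, a shrinkage of 9.6% to 10.5%.

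Varying the effect by visit, with ρ from 0.4 to 0.8:

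- Fading (0.6, 0.5, 0.4): 1.8% to 5.1% for late loss, about 7% to 9% staggered.
- Growing (0.13, 0.27, 0.40): 9.9% to 11.4% for late loss, about 13% staggered.

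**Step 4: simulation.** 184 per arm, 15% missing, constant effect, 20 proper normal imputations with Rubin's rules. Two sets of runs, with 1,500 and 3,000 replicates, are combined as ranges.

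| Analysis | Mean difference | Power |
|---|---|---|
| Within arm, or arm in model | 0.398-0.402 | 94-96% |
| Completers | 0.398-0.403 | 93-95% |
| Arm omitted, interim scores, late loss | 0.371-0.377 | 93-95% |
| Arm omitted, interim scores, staggered loss | 0.359-0.360 | 92-93% |
| Arm omitted, baseline only | 0.338-0.341 | 88-89% |

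**Step 5: how often the rule would act.** The plan names no test, so this is illustration only. A chi-squared test at 0.05 with 184 per arm would trigger the split 5% of the time at 15%/15% missing, 27% at 12.5%/17.5% and 78% at 10%/20%.

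**The case against.** The strongest reply is that the plan never says arm is left out. The rule can be read as a choice between one joint model that contains arm and a separate model for each arm. On that reading shrinkage is zero on both branches. This stands, and it makes the size of the harm conditional. It does not rescue the condition, because the only stated reason for bringing arm in is still the wrong one.

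Second, the primary t-test may use completers. Its description mentions no imputation, power counts only those with outcomes, and the missing-data work is framed as a check on sensitivity. The intention-to-treat statement and the naming of a primary missing-data method point the other way. The documents do not settle it.

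Third, the effect is modest outside the extreme case, and it is conservative. Both are true. With interim scores used, power stays at about 92-95%. The planned mixed-effects analysis of weeks 0 to 12 could also serve as a cross-check, although its terms are not given. Whether the interim scores are in the imputation model is itself unclear. The remark on arbitrary missing patterns may describe the method in general, or the daily device data.

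A reader might infer that the primary result will be biased by 15%. The documents do not support that. It would need the primary test to use imputed data, the pooled model to omit arm, and the interim scores to be unused. The plan states none of these.

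**Conclusion.** The point holds as a fault in a stated rule, and it should be fixed. Association between arm and missingness is not what decides whether imputation must respect arm, and under equal dropout the rule as written withholds its only protection.

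The size depends on what the plan leaves open. There is no shrinkage if arm is in the model. If arm is omitted and the interim scores are used, shrinkage is about 6-10% under a constant effect and roughly 2-13% under fading or growing effects. With baseline variables only it is about 15% (0.40 to 0.34 SD, power about 88-90% instead of about 95%). The last figure follows from the planned 15% missing and would be larger with more dropout or marked imbalance. The intermediate figures depend on the assumed correlations, effect profiles and dropout patterns.

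The bias is toward no effect, so false positives are not inflated. It applies to any imputed comparison by arm, primary or sensitivity. A completer t-test avoids it only if missingness is unrelated to outcome, which is stronger than the plan's missing-at-random assumption.

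**What to change.** Delete the condition in section 15.3. State instead that imputation will always be done within arm, or with arm always in the imputation model, using the week 0, 4 and 8 scores as predictors. State also whether the primary week-12 t-test uses imputed or completer data. Adding the stratification factors (as main effects, since some levels will be small) and Wave is optional.

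The cost is a sentence or two and a few lines of code, with no change to data collection. The loss of precision is negligible: in the staggered-loss simulation at ρ = 0.6, the SD of the estimate was 0.1099 within arm and 0.1095 with arm as a covariate.
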